Flare-up treatment should begin at the onset of the first symptom indicative of a FOP flare-up or substantial high risk traumatic event likely to lead to a flare-up. Participants will be instructed to report potential flare-up symptoms to study site personnel. Symptoms of a FOP flare-up typically include but are not limited to localised pain, soft tissue swelling/inflammation, redness, warmth, decreased joint range of motion, and stiffness (only one symptom is required to define a flare-up). If these symptoms are consistent with previous flare-ups, include a participant-reported onset date, and are confirmed by the investigator as associated with a flare-up, participants will be instructed to immediately begin flare-up-based treatment.

Chronic treatment should cease at the time of initiation of flare-up treatment, re-initiation of the chronic daily treatment should occur after completion of the flare-up treatment.

Flare-ups can occur in the absence of any apparent causative factor, but there is a high risk that substantial traumatic events (e.g. surgery, intramuscular immunisation, mandibular blocks for dental work, muscle fatigue, blunt muscle trauma from bumps, bruises, falls or influenza-like viral illnesses), can lead to a flare-up and result in heterotopic bone formation. Flare-up based treatment should also be initiated if the investigator confirms the presence of a substantial high-risk traumatic event likely to lead to a flare-up.

Persistent flare-up symptoms: treatment may be extended in 4-week intervals with 10 mg palovarotene and continued until the flare-up symptoms resolve.

Intercurrent flare-up: if the participant experiences an intercurrent flare-up (new flare-up location or marked worsening of the original flare-up) at any time during the flare-up treatment, then the 12-week flare-up treatment should be restarted.

In the case of any intolerable adverse reactions, the daily dose of the chronic/flare-up regimen can be reduced (see [Table 5](#)).

Flare-up only regimen:

If the participant experiences intolerable adverse reactions while taking chronic daily treatment and dose reduction does not alleviate the adverse reactions, then the participant may take palovarotene only at the time of flare-up (or substantial high-risk traumatic event).

Visit Frequency:

Every six months.

Study Participant and Intervention Duration:

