from the parent EOS Visit performed outside this allowed time window, assessments will need to be performed again at the Study CLIN-60120-452 Inclusion Visit (flagged with *). However, to enable continued access to the Investigational Product and rollover of participants with impaired mobility [in the case(s) when per investigator's judgement this is considered as beneficial for the participant's medical conditions], the parent EOS Visit and consenting for CLIN-60120-452 and CLIN-60120-452 Inclusion Visit can be conducted remotely. In such case(s) both parts of remote consenting used by the site – i.e. Informing/Consenting discussion and ICF signature should be agreed with the IRB/EC, and the investigator's judgement should be sufficiently documented in the patient source notes.

For the spinal health assessment, a time window of 3 months post parent visit is allowed (flagged with **).

- b. Follow-up Visits will be either in-clinic or performed remotely (e.g. at the participant's home by qualified SP in-home services, and/or via video-conference or telephone contact from clinical site personnel).
- c. The EOS/EW Visit will be ideally an in-clinic visit (or remotely when permitted by the IRB/IEC) and will occur at the time of last study intervention intake. The EOS Visit must take place before the participant transitions to commercial treatment.
- d. For participants <18 years, assent and legal guardian's consent will also be required.
- e. Palovarotene status (treated or not treated) and regimen (chronic or flare-up treatment) at the time of transition to Study CLIN-60120-452 will be collected at the Inclusion Visit. Participants will be supplied with chronic treatment as well as the appropriate dose of palovarotene to initiate flare-up treatment when a flare-up or traumatic event is confirmed by the investigator. Participants will be instructed to report potential flare-up symptoms to study site personnel, only one symptom is required to define a flare-up (see Section 6.1). In the presence of persistent flare-up symptoms, treatment may be extended in 4-week intervals until the flare-up symptoms resolve. If the participant experiences an intercurrent flare-up, or substantial high-risk traumatic event likely to lead to a flare-up, at any time during the flare-up treatment, the 12-week flare-up treatment should be restarted.

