6.1 Study Intervention Administered

The study intervention administered is palovarotene. Participants are eligible for the study whether they are receiving chronic or flare-up treatment in the parent study at the time of transition. Participants who previously interrupted/stopped palovarotene treatment and are currently under parent study follow-up are also eligible if they meet eligibility criteria. As this is a rollover study with the aim of providing treatment continuity, the dose of palovarotene administered will be individualised for each participant and based on the regimen (chronic or flare-up treatment) and the dose they received during their participation in the parent study at the time of transition to Study CLIN-60120-452 or prior to interrupting/stopping palovarotene treatment (to allow for dose modifications made to the standard chronic/flare-up regimen during the parent study).

In the completed parent studies PVO-1A-202/PVO-1A-204 and PVO-1A-301, participants received the chronic/flare-up regimen detailed in [Table 4](#) below (or the weight-based equivalent for <90% skeletally immature participants), with flare-up treatment extension in 4-week increments for persistent symptoms. In Study PVO-1A-301, anytime during flare-up treatment, the 12-week treatment restarts if the participant has another flare-up or a substantial high-risk traumatic event. In both parent studies, the daily dose of palovarotene can be reduced if the participant experiences AEs that are not tolerated.

Participants receiving flare-up treatment at the time of transition to Study CLIN-60120-452 will continue and complete the flare-up treatment as was planned in the parent study. Chronic daily treatment should then be re-initiated at 5 mg, or the dose received during participation in the parent study prior to the flare-up.

Treatment initiation (at the Inclusion Visit) for Study CLIN-60120-452 should ideally concur with the EOS Visit and the study intervention administration schedule of the parent study in order to ensure palovarotene treatment continuity for both chronic and flare-up treatment.

Details of the study intervention are provided in [Table 4](#).

Table 4 Study Intervention Administered

Intervention Name	Palovarotene
Intervention Description	Palovarotene hard capsules, taken once daily as chronic/flare-up treatment
Type	Drug
Dose Formulation	Capsule

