Route of Administration	Oral
Use	Active study intervention
IMP and NIMP/AMP.	IMP
Sourcing	Centrally by sponsor

Packaging and Labelling	
Study intervention will be provided in bottle or blister packaging:
 
 - 90 capsules packaged in a bottle (1 mg, 1.5 mg, 2.5 mg, 5 mg and 10 mg). - 14 capsules packaged in a blister (1 mg, 1.5 mg and 5 mg) - 15 capsules packaged in a bottle (5 mg) for US patients only. 
Each carton will be labelled as required per country requirement.

Storage requirements	To be stored at room temperature (between 15°C and 30°C) and protected from light and humidity.
Former Names/Alias(es)	None

AMP=auxiliary medicinal product; FOP= fibrodysplasia ossificans progressiva; IMP=investigational medicinal product; NIMP=non investigational medicinal product.

Participants will be instructed to report potential flare-up symptoms to study site personnel. Only one symptom is required to define a flare-up. If these symptoms are consistent with previous flare-ups, include a participant-reported onset date, and are confirmed by the investigator as associated with a flare-up, participants will immediately begin flare-up-based treatment. Flare-up based treatment should also be initiated if the investigator confirms the presence of a substantial high-risk traumatic event likely to lead to a flare-up.

Based on clinical signs and symptoms as determined by the investigator, flare-up treatment may be extended in 4-week intervals while on-treatment with 10 mg palovarotene and continue until the flare-up resolves and the 4-week extension treatment has been completed.

Participants will be supplied with chronic treatment as well as the appropriate dose of palovarotene to initiate flare-up treatment when a flare-up or traumatic event is confirmed by the investigator (during in-clinic or remote visit, or by telephone contact).

Participants will be instructed to contact study site personnel immediately in case of intolerable adverse reactions during palovarotene treatment. The investigator will assess the adverse reaction and, if appropriate, will instruct the participant to reduce the daily dose of palovarotene as described in Section 6.5. If the participant does not have the appropriate dose in his/her possession, the study site will make immediate arrangements to ship the appropriate palovarotene dose to the participant.

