## 2.6 Change from Statistical Section of the Protocol

As per section 9.4.1 of the protocol it stated that all analyses will be performed by parent study (PVO-1A-301 or PVO-1A-202/PVO-1A-204), by palovarotene status at the time of transition to Study CLIN-60120-452 (treated, not treated) and treatment regimen (chronic treatment only, flare-up treatment only, chronic & flare-up treatment) and overall.

However, all analyses will only be performed overall and by treatment regimen (chronic treatment only, flare-up treatment only, chronic & flare-up treatment).

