### **5.1.1 Outputs Presentation**

#### *5.1.1.1 Tables Header*

All summary tables will be presented overall and by treatment regimen.

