##### Treatment Regimen

- Chronic Treatment Only
- Flare-up Treatment Only
- Chronic and Flare-up Treatment
- Not Treated (Only required on outputs not using FAS/SAS)

The treatment regimen will be derived from the dosing form collected in CLIN-60120-452 study. All dosing records will be used. Cases where the treatment regimen is not available from the CRF will be discussed with the IPSEN team on a case-by-case basis.

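### The SAP's regimen columns are formed from dosing after Inclusion, so by-regimen flare-up counts and rates, and flare-associated bone growth, are largely set by the grouping itself

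*SAP*

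**What the plan says.** SAP 5.1.1.2 defines the columns Chronic Treatment Only, Flare-up Treatment Only, and Chronic and Flare-up Treatment, and derives them as follows: "The treatment regimen will be derived from the dosing form collected in CLIN-60120-452 study. All dosing records will be used". SAP 5.1.1.1 applies them throughout: "All summary tables will be presented overall and by treatment regimen". SAP 5.7.1 and 5.8.1 repeat this for the primary and secondary endpoints and for safety.

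Protocol 9.4.1 also planned breakdowns by parent study and by palovarotene status at transition, both fixed at entry. SAP 2.6 removes them: "all analyses will only be performed overall and by treatment regimen". Protocol 9.4.1 lists the same three regimen labels but does not say when regimen is determined. The all-records rule comes from the SAP.

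The protocol gives three routes to flare-up dosing:
- **A flare-up.** Protocol 1.1: "Flare-up treatment should begin at the onset of the first symptom indicative of a FOP flare-up". Protocol 6.1 says that once the investigator confirms it, "participants will immediately begin flare-up-based treatment".
- **Trauma without a flare-up.** Protocol 6.1: "Flare-up based treatment should also be initiated if the investigator confirms the presence of a substantial high-risk traumatic event".
- **A cycle already running at entry.** Protocol 6.1: "Participants receiving flare-up treatment at the time of transition to Study CLIN-60120-452 will continue and complete the flare-up treatment".

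SAP 5.7.3.7 summarises flare-up numbers, durations summed per participant, and individual and global monthly rates. SAP 5.7.3.8 summarises the percentage of participants with any extra bone growth, whether or not linked to a flare-up.

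**The concern.** The column a participant ends up in is known only after follow-up, and the main event that moves someone out of 'chronic only' is a treated flare-up. Tabulating flare-ups by that column conditions the outcome on itself. Length of follow-up also drives membership, since a longer stay gives more chance of a first treated flare-up. Stays differ because participants leave when local reimbursement or another access programme arrives, or in November 2024 at the latest.

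'Flare-up Treatment Only' has a related problem. Someone on that regimen who never has a trigger takes no dose in this study, and so is outside the FAS/SAS.

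At stake is how the report is read. A table showing almost no flare-ups under chronic dosing and many under chronic plus flare-up dosing looks like a difference between regimens, but the grouping rule alone would produce it.

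**Working it through.** The plan has no figure to reproduce: there is no power calculation, and 87 is an eligibility ceiling. The documents give no in-study flare-up rate, so every rate below is an assumption. Everyone is given the same true rate, so any difference between columns comes from the grouping.

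**1. Closed form.** Assume Poisson flare-ups at rate r, common follow-up T, every flare-up treated, and no other trigger.
- Share in 'chronic only' = exp(−rT), with an observed rate of 0.
- Mean rate in 'chronic and flare-up' = r / (1 − exp(−rT)).

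| r (per year) | T (years) | 'Chronic only' share | Rate in the other column (per year) | Inflation |
|---|---|---|---|---|
| 1 | 0.5 | exp(−0.5) = 61% | 1/0.393 = 2.54 | 2.5 |
| 1 | 1 | exp(−1) = 37% | 1/0.632 = 1.58 | 1.6 |
| 1 | 2 | exp(−2) = 14% | 1/0.865 = 1.16 | 1.16 |
| 1 | 3 | exp(−3) = 5% | 1/0.950 = 1.05 | 1.05 |
| 0.5 | 1 | exp(−0.5) = 61% | 0.5/0.393 = 1.27 | 2.5 |

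The inflation shrinks as follow-up grows, but the zero in 'chronic only' does not.

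**2. Unequal follow-up and blurred groups.** This is a simulation of 400,000 virtual participants per scenario, with follow-up uniform over 6 to 36 months. The blurred case assumes that 80% of flare-ups are treated, that trauma-triggered dosing occurs at 0.01 per month, and that 10% of participants enter in a running cycle. Rates are per month.

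| True rate | All treated, no other trigger: chronic only / chronic and flare-up | Blurred: chronic only / chronic and flare-up | Ratio in blurred case | 'Chronic only' with any flare-up (blurred) |
|---|---|---|---|---|
| 0.03 | 0 / 0.059 | 0.006 / 0.046 | 7.8 | 10% |
| 0.06 | 0 / 0.081 | 0.012 / 0.075 | 6.3 | 18% |
| 0.12 | 0 / 0.131 | 0.024 / 0.130 | 5.4 | 28% |

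Blurring softens the artefact but leaves a spurious 5- to 8-fold ratio.

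**3. Column size.** With 36 months of follow-up for all and every flare-up treated, the 'chronic only' share is exp(−1.08) = 34%, exp(−2.16) = 12% and exp(−4.32) = 1% at the three rates. That is about 30, 10 and 1 of 87.

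**4. Adverse events unrelated to flare-ups.** Assume an equal risk of 0.03 per month for everyone, a flare-up rate of 0.06, and all flare-ups treated. Incidence is 38% in 'chronic only' and 48% in 'chronic and flare-up', because mean follow-up is 16.7 and 23.0 months. With follow-up fixed at 36 months it is 66% in both. This is a follow-up effect and not circularity.

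**5. Grouping by an entry variable.** With 10% on flare-up dosing at transition, assumed unrelated to later flare-ups, both entry groups show a flare-up rate of 0.060 and an adverse event incidence of about 45%. This shows that the artefact goes. It does not show that real entry groups would have equal disease activity.

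**The case against.** The study is noncomparative and nothing is tested. The Overall column comes first in the group order and is untouched. The harm is therefore limited to misleading descriptive columns. All of that stands, and it sets the weight of the point.

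Four stronger readings are tempting, and the documents do not support them.
- **Safety results by regimen are circular.** This is too strong. SAP 5.7.2.2 also gives the adverse event overview, TEAEs by SOC and PT, maximum intensity, worst causality, discontinuation and dose change by dose at onset, and serious TEAEs likewise. These tables do not use the participant-level column. The cover is partial: the non-serious TEAE tables have no by-dose version, and protocol 8.1.7 makes bone growth and mobility loss after a flare-up adverse events, so part of the count follows the grouping event.
- **All flare-up results are inflated.** SAP 5.7.3.7 uses participants with a flare-up at that visit as the denominator for percentages. Those for location, cause, symptoms and outcome are already conditional on a flare-up. The artefact concerns counts, summed durations and rates.
- **'Chronic only' is exactly the flare-free group.** Untreated or retrospectively reported flare-ups can stay in it, and trauma-triggered or carried-over cycles move flare-free participants out.
- **Regimen at transition could replace the columns.** Protocol Table 1, footnote e records "Palovarotene status (treated or not treated) and regimen (chronic or flare-up treatment) at the time of transition to Study CLIN-60120-452". That is a momentary state. It does not yield the three categories, and it leaves participants who had stopped treatment unplaced.

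The size also depends on the assumed rate and follow-up. The documents state a maximum of three years and the reasons for leaving, but no minimum stay.

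**Conclusion.** The point holds for by-regimen flare-up counts, durations summed per participant, individual and global rates, and the flare-associated part of the extra bone growth percentage. These are largely determined by the all-records grouping, whatever the true rate. At an assumed 1 per year with every flare-up treated, the 'chronic and flare-up' rate is overstated about 2.5-fold at 6 months and 1.16-fold at 2 years, against a rate of zero in 'chronic only'. Under looser assumptions the columns still differ 5- to 8-fold with identical true rates.

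TEAE, CAJIS, FOP-PFQ and PROMIS columns by regimen can be distorted by unequal follow-up and disease activity. For many adverse event tables the dose-at-onset summaries partly address this; the function scores have no such counterpart. The point merits a change to the SAP but does not put the overall results in doubt.

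**What to change.** - **SAP 5.7.3.7 and 5.7.3.8, with matching wording in 5.1.1.2 and 5.1.1.4.** Present flare-up and extra bone growth results overall only, or by a variable fixed at entry, and not by the all-records regimen. Palovarotene status at transition (treated or not treated) is suitable: it is already collected at Inclusion and named in protocol 9.4.1. If it is used, amend SAP 2.6, which drops it.
- **Other tables that keep the all-records columns.** Label them 'regimens received during study', and add a footnote that the groups are formed after Inclusion and are not comparable.
- **TEAEs.** Alongside the by-regimen counts, give rates per time on each regimen or dose. The dosing periods derived in SAP 5.8.2 supply the denominators.

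The cost is SAP and table-shell wording plus some programming, with no new data. The by-regimen flare-up breakdown is lost, and some entry groups may be small. Entry groups may still differ in disease activity, so they too should be read as descriptive.

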#### *5.1.1.3 Presentation of Visits / Timepoints*

Summaries by visit will be presented using the derived window visits (See Section 6.1). Visits in the TFLs will be presented as follows and in the following order:

Visit Name
Baseline
Month 6
Month 12
Month 18
Month 24
Month 30
Month 36

#### *5.1.1.4 Subgroups*

As per section 5.1.1.1 all summaries will be performed by treatment regimen (chronic treatment only, flare-up treatment only, chronic & flare-up treatment).

### **5.1.2 Descriptive Statistics**

All raw and derived variables will be listed and described using summary statistics.

For descriptive analyses, summary statistics will be presented at each scheduled visit and will include sample size, number of available observations (n), number of missing observations

(missing), mean, 95% CIs of the mean/median, standard deviation (SD), median and range for continuous variables. For categorical or discrete variables, the absolute and relative (percentage) numbers based on the non-missing number of observations for each category will be presented, including 95% CIs.

### 5.1.3 *Baseline value*

Unless otherwise specified, baseline is defined as the last non-missing measurement taken prior on the day of first Investigational Medicinal Product (IMP) administration in study CLIN-60120-452. This includes data collected at the Inclusion Visit and data transferred from the final parent study databases (either programmatically or entered by site). See the schedule of assessments in section 2.5 for the method of collection of data for the Inclusion Visit.

### 5.1.4 *Reference Start Date and Study Day*

Reference start date is defined as the day of the first IMP administration of palovarotene (Day 1) in Study CLIN-60120-452. Study day will be calculated as:

- The difference between the event date and the reference date plus one day, if the event is on or after the reference date.
- The difference between the event date and the reference date, if the date of event is prior to the reference date.

Study day will appear in any listings where an assessment date or event date appears.

In case of partial or missing event date, study day will appear missing while any associated durations will be presented based on the imputations described in appendix A3.

## 5.2 Disposition and Analysis Sets

The following disposition summaries and listings will be provided:

- Summary table with the number and percentages of enrolled participants per country, site on the screened set
- Summary table with the number and percentage of participants screened, enrolled, treated, completed, withdrawn and reason for withdrawal on the screened set
- Summary table with the number and percentage of participants per visit on the enrolled set
- Summary table on duration of participant participation in the study on the enrolled set. The definition of the duration of participant participation is from date of consent to the last study visit or date of completion/discontinuation, whichever comes later.
- Listing of dates of visit including duration of participant participation
- Listing of withdrawal participants

In addition, the below summaries and listings will be provided:

- Summary of the number of participants within each treatment regimen subgroup
- Summary of the number and percentages of participants included in each analysis set with reasons for exclusion from each analysis set
- Listing including flag for each analysis set and reason for exclusion from each set

## 5.3 Protocol Deviations

An exhaustive list of major/important protocol deviations that may occur during the course of the study and any action to be taken regarding exclusion of participants from the PP set is defined in Protocol Deviation Plan. Major protocol deviations will be determined and finalised during the data review for the final analysis and documented.

The following protocol deviation summary and listing will be provided on the enrolled set:

- Number and percentage of participants with major protocol deviations by deviation category
- A listing of major protocol deviations.
- A listing of all protocol deviations

